Clinical Trial Protocol: THR-1442-C-481

Study Title: A Phase 1, Open-label, Randomized, Two-period, Two-treatment, Crossover Study to Evaluate the Effect of A High-Fat Meal on the Pharmacokinetics of Bexagliflozin in Healthy Subjects

Study Number: THR-1442-C-481

Study Phase: 1

Product Name: Bexagliflozin Tablets

Indication: Type 2 Diabetes Mellitus

Investigators: Single Center

Sponsor: Theracos Sub, LLC.

Sponsor Contact: [name].
Theracos Sub, LLC.
[name]
[contact]

Sponsor's Protocol Representative: [name].
Translational Medicine Group
Massachusetts General Hospital
[name]
[contact], [contact]
Email: [contact]

Medical Monitor: [name].
Massachusetts General Hospital
[name]
[contact], [contact]
E-mail: [contact].

Date

Version 2: 20 May 2016

Confidentiality Statement

The information in this document is confidential information of Theracos Sub, LLC ("Theracos") and must not be disclosed, used, or copied except with prior written approval from Theracos or to the extent required by applicable local, state or federal laws, rules and regulations.

SYNOPSIS

Sponsor:

Theracos Sub, LLC.

Name of Finished Product:

Bexagliflozin Tablets

Name of Active Ingredient:

Bexagliflozin

Name of Inactive Ingredient:

Polyethylene oxide, glyceryl behenate, lactose monohydrate, micronized poloxamer 188, microcrystalline cellulose, colloidal silicon dioxide, and magnesium stearate.

Study Title:

A Phase 1, Open-label, Randomized, Two-period, Two-treatment, Crossover Study to Evaluate the Effect of A High-Fat Meal on the Pharmacokinetics of Bexagliflozin in Healthy Subjects

Study Number: THR-1442-C-481

Study Phase: 1

Primary Objective:

- To evaluate the effect of a high-fat meal on the pharmacokinetics (PK) of bexagliflozin extended release tablets in healthy subjects.

Secondary Objectives:

- To evaluate the safety of bexagliflozin after a single oral dose in a fasted state and in a fed state in healthy subjects.
- To evaluate the effect of a high-fat meal on the potential pharmacodynamic activity of bexagliflozin by determining urinary glucose excretion in healthy subjects under fasted and fed conditions.

Study Design:

This is a phase 1, single center, open-label, 2 × 2 crossover study designed to assess the effects of a high-fat meal on the PK of orally administered bexagliflozin tablets, 20 mg. Following a ≥ 10-h overnight fast, eighteen (18) eligible healthy subjects will be assigned to two groups with an equal number (n=9) of subjects per group to receive a single oral dose of bexagliflozin tablets, 20 mg, in either a fasted state or 30 min after starting a high-fat meal. A washout period of at least 7 days will be used between the two treatment periods, after which, subjects will receive bexagliflozin tablets, 20 mg, in a fasted or fed state (high-fat), whichever state they had not received previously. The high-fat meal will be ingested in its entirety over an approximate 25-minute period, such that it is completed at least 5 minutes prior to the scheduled time of bexagliflozin dosing for the group receiving bexagliflozin with food. If a portion of the meal is not consumed, the reason and the amount of remaining food

will be recorded. No food should be allowed for at least 4 h after drug administration. Standard meals will be served to both groups 4 hour after dosing.

In treatment period 1, subjects will be admitted to the clinic on day 0, the day before dosing, and will stay in the clinic until 48-h post-dose. In treatment period 2, subjects will be admitted to the clinic on day 7, the day before dosing, and will stay in the clinic until 48-h post-dose. Blood samples for bexagliflozin plasma concentrations will be collected in each period at pre-dose and at 1, 2, 3, 4, 5, 6, 8, 10, 12, 16, 24, 36, and 48 h post-dose. Urine collection in 12 h batches will be performed at pre-dose (-12 to 0 h on day 0 and day 7), and at post-dose at 0 to 12 h, 12 to 24 h, 24 to 36 h, and 36 to 48 h.

Clinical laboratory tests and safety monitoring will be conducted during both treatment periods.

Study Population:

Eighteen healthy subjects are planned to be enrolled and dosed.

Diagnosis and Main Criteria for Inclusion

1. Healthy subjects who are between the ages of 18 and 65 years, inclusive.
2. Subjects with body-mass index (BMI) between 18.0 kg/m² and 32.0 kg/m², inclusive.
3. Male subjects who are surgically sterile or male subjects who are not surgically sterile but who agree to refrain from donating sperm and use appropriate birth control such as the use of condoms when engaging in sexual intercourse for a period of 30 days after discharge from the clinic.
4. Female subjects of childbearing potential who are willing to use an adequate method of contraception and to not become pregnant for the duration of the study. Female subjects who are surgically sterile (hysterectomy, oophorectomy) or postmenopausal (absence of menses greater than 12 months and age > 45 years) are eligible if they test negative on the urine pregnancy test.
5. Subjects who are non-smokers for at least 3 months prior to screening.
6. Subjects with adequate venous access at multiple sites in both arms.

Test Product; Dose; and Mode of Administration:

Bexagliflozin tablets, 20 mg, oral administration.

Duration of Treatment:

Two single dose treatments with at least 7 days apart

Pharmacokinetic Variables:

The following PK parameters of bexagliflozin will be determined where feasible after each subject is dosed with bexagliflozin in a fasted state and 30 min after starting a high-fat meal.

- | | |
|------------------|---|
| C _{max} | Maximum observed plasma concentration |
| T _{max} | Time of maximum observed plasma concentration |
| λ _z | Terminal elimination phase rate constant |
| T _½ | Apparent terminal elimination half-life |

CL/F Apparent oral clearance

V_z/F Apparent volume of distribution

AUC_{0-t} Area under the plasma concentration-time curve from Time 0 to Time t (time of last quantifiable plasma concentration)

$AUC_{0-\infty}$ Area under the plasma concentration-time curve from Time 0 to infinity

Safety Assessments:

- Vital signs
- Clinical laboratory tests including blood chemistry and hematology parameters
- Urinalysis
- Adverse events
- Concomitant medication use

PD Assessment:

- UGE
- Urinary electrolytes, uric acid, and creatinine

Statistical Methods:

Statistical analysis will be performed using Statistical Analysis Software SAS for Windows[®] (SAS Institute Inc., USA). PK parameters of bexagliflozin will be calculated by non-compartmental analysis (NCA) of plasma concentration-time data. Non-compartmental analysis will be performed using Phoenix[®] WinNonlin[®] 6.4 (Certara, USA). To assess the effect of a high-fat meal on the PK of bexagliflozin, an analyses of variance (ANOVA) using a linear mixed-effects model will be fitted to the natural logarithmic transformation of PK parameters of bexagliflozin (C_{max} , AUC_{0-t} and $AUC_{0-\infty}$). The linear mixed-effects model will include subject as a random effect, and treatment, period, and sequence as fixed effects. The 90% confidence intervals will be constructed for the fed : fasted ratio of geometric means of PK parameters (C_{max} , AUC_{0-t} and $AUC_{0-\infty}$), with 80-125% defined as the lack of interaction boundaries.

Descriptive statistics for the PK parameters C_{max} , T_{max} , $AUC_{0-\infty}$, AUC_{0-t} , CL/F, V_z/F , λ_z and terminal elimination half-life ($T_{1/2}$) will be tabulated by treatment. Means, standard deviations, medians, ranges (min, max) and geometric means and coefficients of variation will be presented for all PK parameters with exception of T_{max} . Medians and ranges will be presented for T_{max} .

Descriptive statistics on the PD parameters will be also performed. The effect of high-fat meal on the cumulative UGE between subjects under fasted and fed conditions will be compared.

Date of Original Protocol(V1): 18 May 2016

Prepared in: Microsoft Word 2010

TABLE OF CONTENTS

SYNOPSIS.....	2
LIST OF ABBREVIATIONS AND DEFINITIONS OF TERMS.....	8
1 INTRODUCTION	11
1.1 Bexagliflozin for the Treatment of Type 2 Diabetes Mellitus.....	11
1.2 Summary of Nonclinical Data with Bexagliflozin.....	11
1.3 Summary of Clinical Data with Bexagliflozin.....	11
2 STUDY OBJECTIVES.....	13
2.1 Primary Objective	13
2.2 Secondary Objectives.....	13
3 INVESTIGATIONAL PLAN.....	14
3.1 Overall Study Design and Plan	14
3.2 Rationale for Study Design.....	15
3.3 Study Duration and Dates	15
4 STUDY POPULATION SELECTION	16
4.1 Study Population.....	16
4.2 Inclusion Criteria	16
4.3 Exclusion Criteria	16
5 STUDY TREATMENTS.....	18
5.1 Study Drug.....	18
5.2 Treatments Administered.....	18
5.3 Selection and Timing of Dose for Each Subject.....	18
5.4 Method of Assigning Subjects to Treatment Groups.....	19
5.5 Blinding.....	19

10.2	Institutional Review Board (IRB) or Independent Ethics Committee (IEC) Approval.....	41
10.3	Ethical Conduct of the Study.....	41
10.4	Subject Information and Consent.....	42
10.5	Subject Confidentiality.....	42
10.6	Study Monitoring.....	42
10.7	Case Report Forms and Study Records.....	43
10.8	Protocol Violations/Deviations.....	43
10.9	Access to Source Documentation.....	43
10.10	Retention of Data.....	44
10.11	Publication and Disclosure Policy.....	44
11	REFERENCE LIST.....	45

LIST OF IN-TEXT TABLES

Table 1.	Dosing Schedule.....	18
Table 2.	Required Laboratory Tests.....	23
Table 3.	Blood and Urine Samples.....	24

LIST OF APPENDICES

Appendix 1	Schedule of Events.....	46
Appendix 2	Sponsor Signatures.....	47
Appendix 3	Investigator's Signature.....	48

LIST OF ABBREVIATIONS AND DEFINITIONS OF TERMS

AE	adverse event
ALB	albumin
ALT	alanine aminotransferase
ANOVA	analyses of variance
AST	aspartate aminotransferase
ATC	anatomic therapeutic chemical classification
AUC	area under the time-concentration curve
AUC _{extr}	extrapolated area under the plasma concentration-time curve
AUC _{0-t}	area under the plasma concentration-time curve from Time 0 to Time t
BLOQ	below the limit of quantitation
BMI	body mass index
BP	blood pressure
BUN	blood urea nitrogen
CFR	Code of Federal Regulations
CK	creatinine kinase
C _{last}	concentration corresponding to T _{last}
CL/F	apparent oral clearance
C _{max}	maximum observed plasma concentration
CRF	case report form
CRO	contract research organization
d	day
ECG	electrocardiogram
FDA	Food and Drug Administration
FPG	fasting plasma glucose
GCP	Good Clinical Practice
γ -GTP	gamma-glutamyl transferase
h	hour(s)
HBsAg	hepatitis B surface antigen
HCO ₃	bicarbonate
Hct	hematocrit
HCV	hepatitis C virus
HDL-C	high density lipoprotein cholesterol
Hgb	hemoglobin
HIV	human immunodeficiency virus
IC ₅₀	concentration that produces 50% inhibition of response

ICH	International Conference on Harmonisation
IEC	Independent Ethics Committee
IND	Investigational New Drug
INR	international normalized ratio
IR	immediate release
IRAE	immediately reportable adverse event
IRB	Institutional Review Board
K ₂ EDTA	potassium ethylenediaminetetraacetic acid
λ_z	terminal elimination phase rate constant
LDL-C	low density lipoprotein cholesterol
MCH	mean corpuscular hemoglobin
MCHC	mean corpuscular hemoglobin concentration
MCV	mean corpuscular volume
MedDRA	Medical Dictionary for Regulatory Activities
n	number
NCA	non compartmental analysis
OTC	over-the-counter
PD	pharmacodynamic
PE	physical examination
Pgp	p-glycoprotein
PK	pharmacokinetic
QRS	The QRS complex is a name for the combination of three of the graphical deflections seen on a typical electrocardiogram
QT _c	The corrected QT interval is a measure of the time between the start of the Q wave and the end of the T wave in the heart's electrical cycle
RBC	red blood cell (count)
RR	respiration rate
SAE	serious adverse event
SD	standard deviation
SGLT1	sodium glucose cotransporter 1
SGLT2	sodium glucose cotransporter 2
SOP	standard operating procedure
t _{1/2}	apparent terminal elimination half-life
TBL	serum total bilirubin
TC	total cholesterol
TEAE	treatment emergent adverse events

TG	triglycerides
T _{last}	time of last measurable (positive) concentration
T _{max}	time of maximum observed plasma concentration
UGE	urinary glucose excretion
UGT1A9	UDP glucuronosyltransferase 1 family, polypeptide A9
ULN	upper limit of normal (value)
UTI	urinary tract infection
V _z /F	apparent volume of distribution
WBC	white blood cell (count)
WHO-DD	World Health Organization Drug Dictionary
WOCBP	women of childbearing potential
λ_z	Terminal elimination phase rate constant

1 INTRODUCTION

Bexagliflozin, a potent and selective renal Na⁺/glucose transport protein sodium glucose cotransporter 2 (SGLT2) inhibitor is being developed as a treatment for type 2 diabetes mellitus. The transport of glucose from the renal tubule into the tubular epithelial cells is facilitated by SGLT2 which is expressed primarily in the kidney in the early proximal tubule of the nephron (Washburn 2009). By inhibiting SGLT2, bexagliflozin blocks the reabsorption of filtered glucose, in turn promoting urinary glucose excretion and thereby reducing plasma glucose (Zhang, Welihinda et al. 2011).

Clinical pharmacokinetic (PK) studies have shown that the peak plasma bexagliflozin concentrations occurred between 3 to 5 h and thereafter declined in a biphasic manner with mean elimination half-life values ranging from 7.80 to 9.71 h. Bexagliflozin is cleared predominantly by metabolism to an inactive metabolite, bexagliflozin 3-O-glucuronide by the uridine diphosphate glucuronosyltransferase isoform 1A9 (UGT1A9) pathway. Extended release bexagliflozin tablet formulations are developed to provide greater than 75% release in approximately 8 h *in vitro*. The objective of this study is to evaluate the effects of a high-fat meal on the PK of extended release bexagliflozin tablets, 20 mg.

1.1 Bexagliflozin for the Treatment of Type 2 Diabetes Mellitus

Bexagliflozin is a highly specific inhibitor of SGLT2 with an *in vitro* IC₅₀ of 2 nM or 0.9 ng/mL and a 2435-fold selectivity for human SGLT2 compared with sodium glucose cotransporter 1 (SGLT1). Details of the nonclinical and clinical findings are described in the Investigator's Brochure.

1.2 Summary of Nonclinical Data with Bexagliflozin

Bexagliflozin exhibits high permeability and is a potential Pgp (p-glycoprotein) substrate and inhibitor. It is not a significant inducer or inhibitor of cytochrome P450 isozymes and other transporters relevant for drug-drug interactions.

1.3 Summary of Clinical Data with Bexagliflozin

The early clinical studies have been conducted using immediate release (IR) products in capsules. Theracos has completed multiple phase 1 studies to evaluate safety, tolerability, pharmacokinetics (plasma exposure), pharmacodynamics (glucosuria), and drug metabolism in healthy subjects, patients with type 2 diabetes, and diabetic patients with renal impairment.

Following administration of bexagliflozin IR capsules, time of maximum observed plasma concentration (T_{max}) was reached within 1 to 3 h. The systemic exposure was dose proportional with a maximum observed plasma concentration (C_{max}) of 11 ng/mL per mg bexagliflozin and an area under the plasma concentration-time curve (AUC₀₋₂₄) of approximately 60 ng·h/mL per mg bexagliflozin in healthy or diabetic subjects. Following administration of bexagliflozin tablets in extended release formulations, T_{max} was reached between 3 to 5 h. The tablets produced dose proportional exposure with a C_{max} of 4 or 8

ng/mL per mg bexagliflozin and an AUC_{0-24} of 40 or 50 ng·h/mL per mg bexagliflozin in healthy subjects when dosing was before or after a meal, respectively.

The principal metabolites in humans are similar to those found in monkeys and are dominated by glucuronides of the parent compound, for which the AUC is >30% relative to parent bexagliflozin. Modest accumulation consistent with an extended half-life has been seen following multiple daily dosing. Following oral administration of radiolabeled bexagliflozin, >90% of the ingested radioactivity was recovered, 51% as fecal excretion and 41% as urinary excretion. In urine, bexagliflozin accounts for 1.5% of the dose; most of the radioactivity is excreted as bexagliflozin 3'-*O*-glucuronide. The largest fraction of the radioactivity in feces is due to bexagliflozin, accounting for about 30% of the administered dose.

The safety and tolerability of bexagliflozin in healthy or diabetic subjects was initially evaluated in a single-dose study of up to 100 mg, followed by a 4-week treatment study in which doses ranged from 5 mg/d to 50 mg/d. The most frequently occurring adverse events (AEs) were mild to moderate headache, pollakiuria, nausea, and fatigue. No symptomatic hypoglycemia was reported and no treatment-related adverse event led to discontinuation of treatment. Extended release tablets of 3 mg to 90 mg strengths were well tolerated in a Japanese population with few adverse events reported.

Detailed information of bexagliflozin clinical experience and potential risks for study subjects are provided in the Investigator's Brochure.

2 STUDY OBJECTIVES

2.1 Primary Objective

To evaluate the effect of a high-fat meal on the pharmacokinetics of bexagliflozin extended release tablets in healthy subjects.

2.2 Secondary Objectives

To evaluate the safety of bexagliflozin after a single oral dose in fasted or fed state in healthy subjects.

To evaluate the effect of a high-fat meal on the potential pharmacodynamic activity of bexagliflozin by determining urinary glucose excretion in healthy subjects under fasted and fed conditions.

3 INVESTIGATIONAL PLAN

3.1 Overall Study Design and Plan

This single center, phase 1, open-label, 2×2 crossover study is designed to assess the effects of a high-fat meal on the PK of orally administered bexagliflozin tablets. Eighteen eligible healthy subjects will be randomized into two groups such that an equal number ($n=9$) of subjects will receive a single oral dose of a bexagliflozin tablets, 20 mg, with or without a meal on treatment day 1. Subjects randomized to receive bexagliflozin tablets with a high-fat meal on day 1 will receive a second dose of bexagliflozin tablets without a meal on treatment day 8 after an overnight fast. Subjects randomized to receive bexagliflozin tablets without a meal on treatment day 1 after an overnight fast will receive a second dose of bexagliflozin tablets with a high-fat meal on treatment day 8.

Bexagliflozin will be taken orally with 240 mL of water in the morning (approximately 8 a.m. to 10 a.m.). The time of dosing for a given subject will be the same (as far as practicalities permit) in both treatment periods.

The high-fat meal will follow the FDA guidance (Food Drug Administration 2002) on high-fat (50% of total caloric content of the meal) and high-caloric (800 to 1000 cal) content. An example of the high-fat meal would be two eggs fried in butter, two strips of bacon, two slices of toast with butter, four ounces of hash brown potatoes and eight ounces of whole milk. Substitutions in this meal can be made as long as the meal provides a similar amount of calories from protein, carbohydrate, and fat and has comparable meal volume and viscosity.

Subjects dosed in the fed state will receive an oral bexagliflozin tablets, 20 mg, 30 min after starting to consume a high-fat meal after an overnight fast. No additional food should be allowed for at least 4 h post-dose. Water will be allowed as desired except for one hour before and after drug administration. The meal will be ingested in its entirety over an approximate 25-minute period, such that it is completed at least 5 minutes prior to the scheduled time of bexagliflozin dosing for the fed state treatment. If a portion of the meal is not consumed, the reason and the amount of remaining food will be recorded. Subjects should receive standard meals scheduled at the same time in each period of the study.

Subjects dosed in the fasting state will receive an oral bexagliflozin tablets, 20 mg, after an overnight fast. No food should be allowed for at least 4 h post-dose. Water will be allowed as desired except for one hour before and after drug administration. Subjects should receive standard meals scheduled at the same time in each period of the study.

Subjects will be admitted to the clinic on day 0 and day 7, the day before dosing in each treatment period, and will stay in the clinic until 48-h post-dose. Standard meals will be served at the clinic during the stay. Blood samples (2 mL) for bexagliflozin plasma concentrations will be collected at 0 h (pre-dose), and at, 1, 2, 3, 4, 5, 6, 8, 10, 12, 16, 24, 36, and 48 h post-dose (days 1-3 in treatment period 1 and days 8-10 in treatment period 2 respectively). Urine collection in 12 h batches will be performed at pre-dose (-12 to 0 h on day 0 and day 7), and at post-dose at 0 to 12 h, 12 to 24 h, 24 to 36 h, and 36 to 48 h.

Clinical laboratory tests and safety monitoring will be conducted during both treatment periods.

For the Schedule of Events table, see [Appendix 1](#). For the overall Dosing Schedule, see [Table 1](#).

3.2 Rationale for Study Design

The PK profile of bexagliflozin formulated as an extended release product at 10 and 30 mg has been evaluated in an early clinical trial (THR-1442-C-445). The effects of dose administration in the fasted and fed states were assessed in healthy Japanese subjects for absorption, distribution, metabolism and excretion of bexagliflozin. Twelve subjects were randomized evenly to two dose groups (10 and 30 mg). Each group received first dose of bexagliflozin tablets under fed state on day 1, then after 7-day washout, subjects received second dose under fasted state. The administration of bexagliflozin at 10 and 30 mg with a standard meal resulted in increased average C_{max} (range 39% to 59% for bexagliflozin and 19% to 28% for bexagliflozin 3-O-glucuronide) and decreased half-life (range 23-40% for bexagliflozin and 10% to 21% for bexagliflozin 3-O-glucuronide). However, no meaningful change in the T_{max} of either analyte was observed. No effect of food on the overall systemic exposure [area under the plasma concentration-time curve (AUC)] of bexagliflozin and bexagliflozin 3-O-glucuronide was observed.

In general, meals that are high in total calories and fat content are more likely to affect the gastrointestinal physiology and thereby result in a maximal effect on the bioavailability of a drug substance. Therefore, a high-fat meal will be used in this study to evaluate the potential maximum effect of food on the PK of bexagliflozin tablets, 20 mg, which is the intended commercial product. The planned sample size in this crossover study will be powered to provide sufficient data for a statistical testing of food effect on the PK of bexagliflozin. The results will provide a guide for the timing of dosing relative to meals for this bexagliflozin product.

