9.2 Determination of Sample Size

The sample size for this study is not based upon formal statistical consideration. The sample size is considered adequate to characterize the PK of bexagliflozin, to assess potential food-drug interactions, and to provide safety and tolerability data on bexagliflozin when administered with food (Food and Drug Administration 2002).

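### Does the conflicting wording on whether 18 subjects is a powered sample size, with no stated rule for a split Cmax/AUC result, call for a change?

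*Protocol*

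**What the plan says.** On the sample size, the rationale in Protocol 3.2 states: "The planned sample size in this crossover study will be powered to provide sufficient data for a statistical testing of food effect". Protocol 9.2 states: "The sample size for this study is not based upon formal statistical consideration". SAP 3.5 says the same and calls 18 sufficient, and SAP 3.3 rules out formal hypothesis testing. Neither document gives a target power, an assumed ratio or a within-subject CV.

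On the analysis, Protocol 9.5 and SAP 7.2 specify a mixed model on the log scale for Cmax, AUC0-t and AUC0-∞. Each gets a fed:fasted ratio of geometric means with a 90% CI, set against 80-125% as the limits for lack of interaction. SAP 7.2 also reports the intra-subject CV.

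On earlier data there are two accounts. Protocol 3.2 says dosing "with a standard meal resulted in increased average C_{max} (range 39% to 59% for bexagliflozin" and, for AUC, "No effect of food on the overall systemic exposure". Protocol 1.3 says "The tablets produced dose proportional exposure with a C_{max} of 4 or 8" ng/mL and an AUC0-24 of 40 or 50 ng·h/mL "per mg bexagliflozin in healthy subjects when dosing was before or after a meal, respectively".

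**The concern.** Two things look wrong.

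First, a sample size cannot be both powered for a test and chosen without formal calculation, in a study that plans no formal test. A reader of 3.2 alone would expect a calculation that does not exist.

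Second, the protocol's own history points to a split result. Every earlier Cmax ratio is above 1.25, while AUC is either unchanged (3.2) or at 50/40 = 1.25 (1.3). Section 3.2 also chooses a high-fat meal because such meals are more likely to "result in a maximal effect on the bioavailability of a drug substance". Yet one pair of limits serves three parameters, with no statement on whether they are a criterion or a reference, or whether they are read singly or jointly. The same data could be reported as lack of interaction not shown, or as shown for AUC only. Section 3.2 says "The results will provide a guide for the timing of dosing relative to meals for this bexagliflozin product", SAP 1 describes its methods as flexible, and the study is open-label, so the reading might be picked once results are known.

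**Working it through.** **1. Nothing to reproduce.** The documents give 18 subjects (Protocol 3.1) and at least 8 evaluable per group, so 2 × 8 = 16 (Protocol 5.4). No planned power is stated that the design could miss.

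**2. Set-up.** Balanced 2×2 crossover, log scale:
- σ_w = √ln(1 + CV²)
- SE of the log ratio = σ_w·√(2/n)
- df = n − 2, t at the 95th percentile
- The CI is inside the limits when the estimate lies between ln 0.80 + t·SE and ln 1.25 − t·SE. The probability is integrated over the chi-square distribution of the residual variance.
- The chances that the CI excludes 1, or lies wholly above 1.25, come from the noncentral t.

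CV is an assumption, taken as 15% to 40%. Example at CV 30%, n = 18: σ_w = √ln 1.09 = 0.2936; SE = 0.2936 × √(2/18) = 0.0979; t(16) = 1.746; CI half-width factor exp(1.746 × 0.0979) = 1.186.

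**3. Results for n = 18.**

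| CV (assumed) | Cmax 1.39: CI inside 80-125% | Cmax 1.39: CI excludes 1 | Cmax 1.39: CI wholly above 1.25 | AUC 1.00: CI inside 80-125% |
|---|---|---|---|---|
| 15% | 0.01% | >99.9% | 65.5% | 99.2% |
| 20% | 0.07% | 99.9% | 45.8% | 88.8% |
| 25% | 0.20% | 98.6% | 34.2% | 66.1% |
| 30% | 0.35% | 94.2% | 27.2% | 41.3% |
| 35% | 0.47% | 87.2% | 22.7% | 21.9% |
| 40% | 0.46% | 79.1% | 19.7% | 10% |

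- Over CVs from 2% to 80%, containment at a Cmax ratio of 1.39 peaks at 0.48% (n = 18) or 0.50% (n = 16). At 1.59 the peak is 0.03%.
- At 1.59 the CI excludes 1 with probability at least 96% for CV up to 40% (n = 18).
- For AUC at a true ratio of 1.00, containment reaches 80% at CV 22.1% (n = 18) or 20.7% (n = 16). At a true ratio of 1.25 it is 5% or less.

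**4. What the Cmax figures mean.** A 90% CI held inside limits amounts to two one-sided 5% tests. A pass rate of at most 5% at or beyond 1.25 is therefore the definition of the procedure. It measures no harm from the wording in 3.2 or from the missing joint rule.

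**5. The two AUC accounts.** Section 1.3 gives AUC0-24; section 3.2 speaks of overall exposure. Section 3.2 also reports that food shortened half-life by 23% to 40%, so more of the fasted AUC falls after 24 h. As an illustration, assume mono-exponential decline and equal total AUC. The share reached by 24 h is then 1 − exp(−24·ln 2/T½). Half-lives come from the range of 7.80 to 9.71 h in Protocol 1.
- Fasted 7.80 h, fed 7.80 × 0.77 = 6.01 h: 0.937/0.881 = 1.06
- Fed 9.71 h, fasted 9.71/0.60 = 16.18 h: 0.820/0.642 = 1.28

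An AUC0-24 ratio of 1.25 can therefore coexist with no effect on total AUC. Rounding to tens alone allows 45/45 = 1.00 to 55/35 = 1.57.

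**6. What the report will hold.** Under any reading of the limits, SAP 7.2 produces three ratios, three 90% CIs and the intra-subject CV. None of these depends on whether the limits are called a criterion or a reference.

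**The case for a change.** The strongest case for acting is that the texts do conflict and one sentence would settle each point. Containment of Cmax is close to impossible at the protocol's own ratios whatever the sample size, so a calculation for that criterion could not make good the claim in 3.2. A joint reading of the three parameters would almost always end in lack of interaction not shown, whatever AUC did. Fixing the reading in advance costs only words.

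The conflict between 3.2 and 9.2 stands. The rest carries less weight.

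- Section 3.2 speaks of testing for a food effect. Its natural sense is finding an effect, and for that 18 subjects do well (79.1% to over 99.9% at 1.39).
- Nothing in Protocol 9.5 or SAP 7.2 suggests a joint requirement. Both set out a ratio and CI per parameter, and with SAP 3.3 the plain reading is estimation, one parameter at a time.
- SAP 1 requires a sound rationale for any deviation. SAP 4 has the plan finalised before database lock and analysis, and SAP 10 requires changes to be documented before lock or identified in the study report. That is not complete protection, but a change of reading would have to be declared.
- The earlier ratios are weak planning values: twelve subjects, six per dose, 10 and 30 mg, a standard meal, and everyone dosed fed first, so food is confounded with period. No CI is given. The figures in 1.3 are rounded and not said to be within-subject.

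**Conclusion.** No change is called for. The description in Protocol 3.2 is a clerical slip: 9.2, SAP 3.5 and SAP 3.3 agree with each other, and no result depends on the odd sentence. The missing rule for a split result is a gap that analysts would fill in the ordinary way, by reporting Cmax and AUC separately against the limits. Comparing a CI with limits is compatible with SAP 3.3.

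A split result is plausible, and the planned output would show it. If Cmax truly rises by 39% or more, its CI will almost never sit inside 80-125% (at most 0.5% with 16 to 18 subjects), which is the right answer. AUC would pass with at least 80% probability if its true ratio is 1.00 and the CV is no more than 22.1% (n = 18) or 20.7% (n = 16).

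These figures rest on a balanced crossover with complete data and on assumed CVs. The Cmax containment bound holds across all CVs scanned (2% to 80%). Sample size, model, ratios and CIs are unaffected.
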